(ii) Sevelamer: This agent is a non-absorbable, cross-linked polymer that has strong LPS-binding capacity, and therefore limits intestinal wall translocation of LPS (41). Sevelamer also has affinity for phosphates and it is FDA-approved for use as a phosphate binder in patients with chronic kidney disease. Sevelamer does not cause hypophosphatemia in individuals with normal kidney function (42, 43). We have confirmed sevelamer's ability to reduce LPS concentration *in vitro* and to inhibit LPS-induced inflammatory response using our primary

human muscle cell culture system and isolated rat muscle preparation (Fig.12). A cross-sectional study found that subjects who take sevelamer have lower LPS concentration (35) and prospective studies have shown that sevelamer reduces LPS concentration in humans as much as 80% (36, 37). We have confirmed sevelamer's LPS-lowering effect in our study population (Fig. 11). Based upon its ability to sequester LPS in the intestinal lumen, sevelamer's systemic anti-inflammatory and immune-modulating properties are being tested in a large NIH-sponsored multi-center (20 academic sites) trial, in otherwise healthy HIV-infected subjects with normal renal function (<https://actgnetwork.org>).

[figure not shown]

Figure 14. Study design (Aim 1)

**Subjects.** 36 (completers), healthy, lean (BMI <26 kg/m^2) normal glucose tolerant subjects, aged 18-65 years, without a family history of T2DM, will be enrolled (50% males). Subjects will be randomized to receive a low or a high fat diet for 4 weeks. After a 10-12 week washout period, subjects who first received the low fat diet, will then receive the high fat diet for 4 weeks, and vice versa (each subject will be its own control). During the time the subjects receive these diets, they will simultaneously receive in a randomized double-blind fashion (i) placebo, (ii) synbiotic or (iii) sevelamer (n=12 completers per group). The protocol is outlined in Fig. 14.

**Inclusion Criteria:** 1) Both genders. All races and ethnic groups.

2) Premenopausal women in the follicular phase, non-lactating, and with a negative pregnancy test.

Postmenopausal women on stable dose of or not exposed to hormone replacement for ≥6 months.

3) HCT ≥ 34%, serum creatinine ≤ 1.4 mg/dl, electrolytes, urinalysis, and coagulation tests. LFTs up to 2X.

4) Stable body weight (±2%) for ≥ 3 months. Two or less sessions of strenuous exercise/wk for last 6 months.

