collected in the postprandial state, and this will allow us to evaluate acute postprandial changes in chylomicron LPS content and plasma LPS level, and how these relate to measures of insulin action.

**Specific Aim 2) To determine whether microbiome modulation and an experimental reduction in plasma LPS concentration improve inflammation and insulin action in insulin resistant (obese and T2DM) subjects.**

**Rationale.** Obese and T2DM subjects have alterations in the intestinal microbiome (lower content of beneficial bacteria such as Bifidobacteria) (5), abnormal gut permeability (24, 53), increased plasma LPS (preliminary data) (54, 55), and elevated TLR4 signaling in muscle (38) and monocytes (56). In this Aim we will test whether protecting the intestinal barrier with a synbiotic will restore normal gut permeability, reduce LPS, and ameliorate inflammation (TLR4 signaling) and insulin resistance. To assess the role of LPS independently, also we will reduce plasma LPS concentration with sevelamer.

**Subjects.** 36 (completers) lean ( $BMI < 26 \text{ kg/m}^2$ ) normal glucose tolerant, 36 (completers) obese ( $BMI = 30-37$ ) normal glucose tolerant, and 36 (completers) obese ( $BMI = 30-37$ ) T2DM subjects will be studied. 12 subjects per group will receive the synbiotic (oligofructose plus Bifidobacterium longum), 12 sevelamer, and 12 placebo. We will study an equal number of males and females. Other inclusion and exclusion criteria are similar as described in Aim 1, except that T2DM subjects ( $Hb_{A1c} \leq 8.5\%$ ) will be enrolled. The only antidiabetic drugs allowed are sulfonylureas, due to their minimal effect on muscle physiology and inflammation. Sulfonylureas will be held for 48 h before any procedure to avoid hypoglycemia during fasting.

**Design. Visit 1:** Subjects will undergo a medical history, physical examination, and screening blood tests.

**Visit 2:** Within 3-14 days eligible subjects will return for OGTT.

**Visit 3:** Within 3-14 days subjects undergo blood (LPS) and stool collection and an intestinal permeability test.

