TLR4 regulates numerous signaling cascades, including IKK/NF $\kappa$ B, JNK, ERK, p38 and SOCS. One or more branches downstream of TLR4 might be responsible for the negative effect of LPS on glucose metabolism. Dissecting the role of each of these branches in LPS-induced insulin resistance is beyond the scope of this grant application. Nonetheless, using our primary cell culture system and shRNA, in the future we could perform an in-depth analysis about the contribution of each of these signaling branches.

**Statistical analysis.** Experimental results will be expressed as means  $\pm$  SE. Comparisons of means between all the groups will be done by ANOVA for repeated measures (67). Associations between measures of LPS concentration vs. TLR4 signaling and vs. insulin signaling/sensitivity, within a group, will be determined by Pearson's correlation. For tests of correlation coefficients between groups we will use the Fisher's Z transformation (64). We will also determine the relationship between plasma LPS concentration vs. TLR4 signaling and LPS vs. insulin signaling/sensitivity, by using multiple regression analysis. Scatter plots will be done to look for outliers and to verify linearity. [name] is an experienced biostatistician who will direct the statistical analysis of this study. Based on our preliminary results and data from the literature (36, 65) regarding the variability of these measurements, we calculated that an  $n=12$  subjects/group is required to obtain power  $(1-\beta)$  of 0.80 with a 2-sided test at  $\alpha=0.05$  significance level. Assuming a  $\sim 20\%$  dropout rate, 15

subjects/group would be sufficient to achieve the required group sizes. The following data and power analysis (2-tailed) were obtained from an ongoing human study (PI: [name]).

Variable	Mean±SD Lean	N	Mean±SD Obese	n	Power
LPS Concentration	0.049±0.055	12	0.119±0.014	12	0.99
Insulin Sensitivity (M)	11.3±2.8	12	8.1±2.4	12	0.91
Ins Stim IRS1-P-Y	4.0±1.1	12	0.9±0.6	12	0.99
Variable	Mean±SD Lean	N	Mean±SD T2DM	n	Power
LPS Concentration	0.049±0.055	12	0.130±0.071	12	0.99
Insulin Sensitivity (M)	11.3±2.8	12	4.2±1.7	12	0.99
Ins Stim IRS-1 P-Y	4.0±1.1	12	1.5 ±1.0	12	0.99

For the following variables, data were obtained from published human studies (36, 40, 65).

Variable	Mean±SD Pre-Sevel	N	Mean±SD Post-Sevel	n	Power
LPS Concentration	3.6±3.0	12	1.2±2.3	12	0.99
CRP Concentration	4.8±2.4	12	0.44±0.24	12	0.99
Variable	Mean±SD Placebo	N	Mean±SD Synbiotic	n	Power

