**Risks:** a) Muscle biopsy: Local hematomas occur in <2% of subjects. b) Sevelamer: This drug is FDA approved for use as a phosphate binder. Sevelamer does not cause hypophosphatemia in subjects with normal kidney function (71, 76). As a precaution, we will only enroll subjects with normal phosphorus plasma concentration, which will be monitored during treatment. Sevelamer is a very safe drug; its main side effects are gastrointestinal. Subjects with a history of gastrointestinal obstruction and/or surgery within 2 years will be excluded. c) Oligofructose and Bididobacteria administration is very safe. Rarely these can cause bloating.

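### Both aims are sized on completers and compare means by repeated-measures ANOVA with no analysis population or missing-data method, so the main randomised comparison would by default be restricted to completers

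*Combined protocol and SAP*

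**What the plan says.** All places are in section D, Research Design and Methods, of the combined protocol and SAP.

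- **Specific Aim 1, Subjects.** The target is "36 (completers), healthy, lean" subjects. The product arms are "i) placebo, (ii) synbiotic or (iii) sevelamer (n=12 completers per group". Each subject takes the same product in two 4-week diet periods separated by a 10-12 week washout.
- **Specific Aim 2, Subjects.** The targets are again completers: 36 lean, 36 obese and 36 with type 2 diabetes ("36 (completers) obese ( $BMI = 30-37$ ) T2DM subjects will be studied"). Within each cohort, "12 subjects per group will receive the synbiotic (oligofructose plus Bifidobacterium longum), 12 sevelamer, and 12 placebo".
- **Statistical analysis.** Twelve "subjects/group is required to obtain power" of 0.80 at two-sided 0.05. With about 20% dropout, 15 per group are enrolled so that the required sizes are reached. The method for means is: "Comparisons of means between all the groups will be done by ANOVA for repeated measures". Pearson correlation and multiple regression are planned for associations.
- **Metagenomics.** Taxa are compared between diets and treatments by ANOVA, t-tests and non-parametric versions, with generalized linear models for associations.
- **Risks.** For sevelamer: "Sevelamer is a very safe drug; its main side effects are gastrointestinal". The synbiotic is also called very safe, with rare bloating. Side effects of the maltodextrin placebo are not discussed.

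No analysis population and no method for missing data is named in any of these places, and follow-up of a subject who stops the product or diet is not mentioned.

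**The concern.** Product against placebo is the randomised, double-blind test in Aims 1 and 2. Its protection comes from comparing subjects as randomised. A target counted in completers, enrolment raised to reach it, a method that needs complete data, and silence on everyone else together lead by default to a completer comparison.

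Two things are at stake. First, if subjects leave for reasons that differ by arm and relate to outcome, the completers in the arms are no longer comparable. The endpoints include intestinal permeability, the microbiome and LPS, and the side effects listed for the active products are gastrointestinal, so such a link is conceivable. Second, data are lost. An Aim 1 subject who finishes period 1 has had a clamp, two biopsies, permeability testing and stool and LPS sampling. If that subject leaves during the washout, classical repeated-measures ANOVA drops the subject from the comparison of means.

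**Working it through.** **1. The plan's enrolment figure.** Inputs: 12 per group and about 20% dropout (Statistical analysis). 12 / (1 - 0.20) = 15, which reproduces the stated 15. In reverse, 15 x 0.80 = 12.

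**2. Subjects at issue.** Aim 1: 3 arms x 15 = 45 enrolled for 36 completers, so 9 lost. Aim 2: 9 cells x 15 = 135 enrolled for 108 completers, so 27 lost. In both, 3 of 15 per arm (20%).

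**3. Size of a possible selection bias.** Assumptions not in the documents: the true effect is zero; the active arm loses the lowest 3 of 15 on a latent variable that has correlation r with outcome; placebo dropout is random. For a large sample at r = 1, the mean after removing the lowest 20% is 0.2800 / 0.8 = 0.35 SD. With 15 per arm, simulation gives:

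| r | Bias (SD) | Two-sided error rate, nominal 5% |
|---|---|---|
| 0 | 0 | 5.0% |
| 0.3 | 0.10 | about 5.9% |
| 0.5 | 0.16 to 0.17 | about 7.2% |
| 1.0 | 0.33 | about 15% |

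If the same selection acts in both arms, the bias is zero at every r. For scale, 12 per group has 80% power at a difference of about 1.20 SD (noncentral t).

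**4. What a mixed model recovers in Aim 1.** Assumption: all 3 dropouts per arm leave after period 1. Because diet order is randomised, on average 1.5 of them have been seen on a given diet. Let r_w be the correlation between a subject's two periods. Period effects are left out for simplicity.

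- r_w = 0: effective n for one diet is 12 + 1.5 = 13.5. The standard error falls by 1 - sqrt(12/13.5) = 5.7%.
- r_w near 1: the observed period stands in for the missing one, so the effective n approaches 15. The standard error falls by 1 - sqrt(12/15) = 10.6%.

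So the gain for product against placebo on one diet is about 6% to 10.6%. For the within-subject diet difference, and hence product-by-diet, the variance ratio is [12/(1 - r_w)] / [12/(1 - r_w) + 1.5]. At r_w = 0.5 this is 24/25.5, so the standard error falls by only 3.0%, and the gain vanishes as r_w approaches 1.

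**5. Aim 2.** Clamp and biopsies are done before randomisation (Visit 4) and on day 28 (Visit 6). A subject who leaves before day 28 has only a baseline value for these endpoints, so the gain is smaller there. LPS, stool and permeability are also collected on day 24 (Visit 5), so a later dropout can still contribute those.

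**The case against.** The strongest case on the other side is that the plan contains a reporting gap and nothing worse.

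- Completers appear only as a size target, and 12 to 15 is ordinary fixed inflation for dropout. A reader might infer that dropouts are replaced rather than followed, or that results will be reported on completers. Neither is in the text: no replacement is described and no analysis set is named. This stands.
- A reader might infer that a subject who leaves in the washout contributes nothing. That is too strong. The correlation, regression and microbiome analyses do not all need both periods, and Aim 3 uses lean subjects' muscle cells and subjects' sera. The loss is from the repeated-measures comparison of means.
- A reader might infer that no visit is kept for a subject who stops product. The plan is silent. Visits are set by day of intervention, and nothing says that stopping the packets ends participation.
- Differential dropout is not shown. Both products are called very safe, silence about maltodextrin is no evidence that placebo is better tolerated, and sevelamer packets also contain maltodextrin. Diet, clamps, biopsies and study length are common to all Aim 1 arms. The bias figures rest on one-arm selection that the documents do not support. This stands, which is why they are given only as a conditional range.
- The plan calls Aim 2 a proof-of-principle experiment, where emphasis on exposed subjects is defensible. If the 20% who stop were assessed and showed no effect (an assumption), the mean effect would shrink to 0.8 of plan and 12 / 0.8² = 18.75, or 19 per arm, would be needed for the same power. Assessment after stopping is therefore a real trade-off.

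None of this supplies the missing analysis population or missing-data method, and none of it favours classical ANOVA over a model that uses all the data collected.

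**Conclusion.** The concern holds in a limited form. Both aims are sized on completers, the stated method for means excludes incomplete subjects in its classical form, and no analysis population or missing-data method is named. By default the main randomised comparison of means would rest on completers, with up to 20% of each arm left out.

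The documents do not support the stronger reading that the comparison becomes one of subjects selected for tolerance. That would need dropout that differs by arm and relates to outcome, and no dropout by arm is given. Under the assumed active-arm-only selection, the bias is about 0.10 to 0.17 SD and the error rate about 6 to 7% for correlations of 0.3 to 0.5. The 15% error rate needs a correlation of 1. The bias is zero if dropout is unrelated to outcome or acts alike in both arms.

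The efficiency loss needs no bias assumption, but it does depend on when subjects leave. It is about 6% to 10.6% of the between-arm standard error for one diet in Aim 1 if all dropouts leave after period 1, less for the diet contrast, and smaller for clamp and biopsy endpoints in Aim 2.

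**What to change.** In Statistical analysis, replace repeated-measures ANOVA with a likelihood-based mixed model on all randomised subjects as assigned, using every available period or visit:

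- Aim 1: product, diet, period and product-by-diet, with a subject effect, so that subjects with one period stay in.
- Aim 2: product, cohort and visit, with the treatment effect read from product-by-visit.

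State that the completer numbers are sizing targets and not the analysis population. Report dropout with reasons by arm. Give the completer analysis as a sensitivity analysis, which also keeps the mechanistic contrast in view.

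The cost is a change of wording and slightly more analysis work, with no new subjects or procedures. The model relies on data being missing at random, which should be stated. Assessing subjects who have stopped product at the scheduled visits is optional. If the sponsor chooses it, the plan should acknowledge the possible dilution and its effect on power.

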**Interpretation and limitations.** We expect that the obese and T2DM subject will have an unfavorable intestinal microbiome profile (decreases in Bifidobacteria and Bacteroidetes) (54, 55) which will be associated with enhanced intestinal permeability and increased LPS level. Thus, we expect that these subjects will have an elevated inflammatory tone (TLR4 signaling) in muscle, which will reduce insulin action. Based upon previous animal studies (23-25), we anticipate that the synbiotic will restore gut epithelial integrity, decrease circulating LPS level, and ameliorate insulin resistance in obese and T2DM subjects. We also anticipate that sevelamer will decrease LPS concentration (36, 37) and will lead to reduced inflammatory signaling (IKK/NF $\kappa$ B, MAPK, inflammatory genes) in muscle. Because sevelamer's effect is to reduce LPS, also we anticipate that flux through TLR4 (TLR4-MyD88 association) will be lower. In addition, we expect that the reductions in LPS concentration will predict (correlate with) changes (reductions) in TLR4 signaling and improved insulin action.

Aim 1 will test whether a fat-rich diet alters the gut microbiome and disrupts the intestinal barrier in lean subjects resulting in increased LPS translocation. The goal of Aim 2 is different; in this Aim we are proposing a proof-of-principle experiment to evaluate whether modulating the microbiome and lowering plasma LPS improves insulin action in obese and T2DM subjects. We anticipate that modulating the microbiome and plasma LPS concentration will decrease inflammation and insulin resistance in these individuals. If these changes are the result of protection of gut barrier integrity from the increased fat intake which is common in obese and T2DM subjects, then sevelamer and the synbiotic also should prevent the inflammatory response and insulin resistance caused by the high fat diet in the lean subject from Aim 1. If the lean subjects are not protected from the high fat diet, but the obese and T2DM subjects benefit from sevelamer and the synbiotic, then improvements in inflammation and insulin action are likely caused by a mechanism different from protection against fat-induced damage. Other possible mechanisms by which LPS sequestration and/or microbiome modulation could improve inflammation and insulin action include changes in fructose-mediated endotoxemia (57), food energy extraction (9), appetite (10-13), bacterial flagellin levels (14), and peptidoglycans (15).

One limitation of the proposed experiment is that the synbiotic could alter inflammation and glucose metabolism through other mechanisms, such as by inducing changes in the concentration of FFA and cytokines. Sevelamer also could lead to other effects; this agent can bind to uric acid and reduce its plasma concentration (58), although uric acid *per se* generally is not thought to induce insulin resistance. A primary human cell culture system will be employed in Aim 3 which will allow us to test whether the differences in inflammation and insulin sensitivity between groups and the effect of the interventions are due to changes in circulating LPS.

The proposed studies focus on the impact that the gut microbiome and endotoxemia have on inflammation and insulin action at the level of the skeletal muscle. We are focusing on this tissue because it is the main site for insulin-mediated glucose disposal. Nonetheless, the liver, adipose tissue, brain, and inflammatory cells (monocytes) also are potentially subjected to the influence of the microbiome and LPS. Studying these organs/tissues is beyond the scope of this grant, but they are important areas for future investigation.

**Specific Aim 3) To determine whether the LPS present in the sera from lean high fat fed, obese, and T2DM subjects mediates the insulin resistance, and whether this effect is mediated via TLR4. Rationale.**

An *in vitro* system will be employed because it will allow us to directly assess the role of LPS and TLR4 on insulin resistance in human muscle. Testing the effect of sera in cultured cells while blocking the immune mediator of interest is a commonly employed method to assess the independent biological effects of the numerous immune mediators (antibodies, cytokines, etc.) which are altered in patients with immune-mediated diseases (lupus, rheumatoid arthritis) (59). In this Aim we will apply the same concept in view that obesity and T2DM are considered inflammatory (and metabolic) diseases.

**Experimental model.** We will use primary human myotubes developed from the muscle samples obtained in the lean subjects enrolled during Aim 1, as described by our group (38). To avoid experimental variation, myoblasts from all lean subjects will be pooled, aliquoted, and frozen. Prior to each experiment an aliquot will be thawed, cells plated, and differentiated into myotubes. We will use cells from early (2-3) passages.

**Experiment 1. Does sera from lean high fat fed, obese, and T2DM induce inflammation and insulin resistance and are these effects ameliorated by *in vivo* treatment with the synbiotic and sevelamer?**

Human myotubes are treated with sera from (i) lean subjects studied in Aim 1 who ingested a low and high fat diet and received the synbiotic, sevelamer, and placebo; and (ii) lean, obese and T2DM subjects who received the synbiotic, sevelamer, and placebo (Aim 2). Treatments are conducted in a time-dependent (24h and 48h) and dose-dependent (10%, 20% and 40% serum in MEM culture media) manner. After these incubations, cells are collected for measurement of TLR4 signaling (TLR4-MyD88 association, IKK/NFκB, MAPK, inflammatory genes) (38, 48). To assess the effect on insulin action, after treatment with the subjects' serum, cells are stimulated with insulin for 20 min. Cells are then collected in lysis buffer for insulin signaling studies (49) or subjected to a glucose transport assay (60). Increasing concentrations of insulin (0, 1, 10 and 100 nM) will be employed to determine whether the sera affects insulin responsiveness (shifting of the curve).

**Experiment 2. Does elevated LPS in the circulation mediate the inflammatory state and insulin resistance observed in muscle from lean high fat fed, obese, and T2DM subjects?** Serum samples from these subjects will be treated with polymyxin B which sequesters LPS and specifically blocks its biological

activity (61). Polymyxin B cannot be administered to human subjects due to its nephrotoxicity. However, because of its capacity to sequester LPS, ongoing multicenter clinical trials are being conducted assessing the effect of extracorporeal hemoperfusion with polymyxin B absorption columns in patients with sepsis (62). Assays of TLR4 signaling, inflammatory gene expression, insulin signaling, and glucose transport will be conducted in the presence and absence of polymyxin B (20  $\mu\text{g/ml}$ ).

**Experiment 3. Does TLR4 mediate the pro-inflammatory state and insulin resistance observed in lean high fat fed, obese, and T2DM subjects?** Myotubes from lean subjects will be treated with sera from lean high fat fed, obese and T2DM subjects, and the same experiments described in Experiment 1 will be conducted (TLR4 signaling, inflammatory genes, insulin signaling, glucose transport). To test whether the effects from the sera are TLR4-mediated, TLR4 will be blocked/inhibited using two different approaches:

a) **TAK242**: This agent (Takeda Pharmaceuticals) binds specifically to TLR4 and inhibits signaling by preventing its interaction with the adapter proteins TRAM and TIRAP (63).

b) **shRNA**: To knock down TLR4 we will use adenoviral-driven shRNA (Vector Biolabs, Philadelphia, PA) as described by our group (38). As negative control we will use a scrambled non-mammalian sequence (Ad-scrambled). We will perform a dose-response study to determine the minimal amount of virus that will achieve maximal knock down efficient. Based on our own experience, we anticipate that this dose will be in the  $1 \times 10^2$  to  $1 \times 10^8$  PFU/ml range. Fig. 17 shows images of typical human myotubes developed in our lab infected with adenovirus tagged with green fluorescent protein. Figs. 18a and 18b show that our method is highly effective to knock down TLR4.

[figure not shown]

Figure 17.

[figure not shown]
[figure not shown]

Fig. 18b

**Interpretation and limitations.** Based on our preliminary studies (Fig. 13), we anticipate that sera from lean high fat fed, obese, and T2DM will induce an inflammatory response and insulin resistance as evidence by elevated IKK/NF $\kappa$ B and MAPK signaling and inflammatory gene expression, decreased insulin signaling, and decreased glucose transport, as compared with myotubes treated with sera from lean subjects. If our hypothesis is correct, sera from high fat fed, obese and T2DM subjects, collected after treatment with the synbiotic and sevelamer, will induce a less severe inflammatory response and insulin resistance, and the changes in LPS level after *in vivo* treatment will predict the *in vitro* response.

One limitation of this approach is that numerous systemic factors could be responsible for the inflammatory response and insulin resistance caused by sera from high fat fed, obese and T2DM subjects. If these effects are mediated by LPS, its neutralization with polymyxin B should ameliorate them. In addition, if the effect is mediated through TLR4, the inflammatory response and insulin resistance caused by the sera will be reduced/prevented by blocking/downregulating TLR4 with TAK242 and shRNA.

TLR4 regulates numerous signaling cascades, including IKK/NF $\kappa$ B, JNK, ERK, p38 and SOCS. One or more branches downstream of TLR4 might be responsible for the negative effect of LPS on glucose metabolism. Dissecting the role of each of these branches in LPS-induced insulin resistance is beyond the scope of this grant application. Nonetheless, using our primary cell culture system and shRNA, in the future we could perform an in-depth analysis about the contribution of each of these signaling branches.

**Statistical analysis.** Experimental results will be expressed as means  $\pm$  SE. Comparisons of means between all the groups will be done by ANOVA for repeated measures (67). Associations between measures of LPS concentration vs. TLR4 signaling and vs. insulin signaling/sensitivity, within a group, will be determined by Pearson's correlation. For tests of correlation coefficients between groups we will use the Fisher's Z transformation (64). We will also determine the relationship between plasma LPS concentration vs. TLR4 signaling and LPS vs. insulin signaling/sensitivity, by using multiple regression analysis. Scatter plots will be done to look for outliers and to verify linearity. [name] is an experienced biostatistician who will direct the statistical analysis of this study. Based on our preliminary results and data from the literature (36, 65) regarding the variability of these measurements, we calculated that an  $n=12$  subjects/group is required to obtain power  $(1-\beta)$  of 0.80 with a 2-sided test at  $\alpha=0.05$  significance level. Assuming a  $\sim 20\%$  dropout rate, 15

subjects/group would be sufficient to achieve the required group sizes. The following data and power analysis (2-tailed) were obtained from an ongoing human study (PI: [name]).

Variable	Mean±SD Lean	N	Mean±SD Obese	n	Power
LPS Concentration	0.049±0.055	12	0.119±0.014	12	0.99
Insulin Sensitivity (M)	11.3±2.8	12	8.1±2.4	12	0.91
Ins Stim IRS1-P-Y	4.0±1.1	12	0.9±0.6	12	0.99
Variable	Mean±SD Lean	N	Mean±SD T2DM	n	Power
LPS Concentration	0.049±0.055	12	0.130±0.071	12	0.99
Insulin Sensitivity (M)	11.3±2.8	12	4.2±1.7	12	0.99
Ins Stim IRS-1 P-Y	4.0±1.1	12	1.5 ±1.0	12	0.99

For the following variables, data were obtained from published human studies (36, 40, 65).

Variable	Mean±SD Pre-Sevel	N	Mean±SD Post-Sevel	n	Power
LPS Concentration	3.6±3.0	12	1.2±2.3	12	0.99
CRP Concentration	4.8±2.4	12	0.44±0.24	12	0.99
Variable	Mean±SD Placebo	N	Mean±SD Synbiotic	n	Power
LPS Concentration	87±14	12	54±10	12	0.99

We performed the following calculations (two-tailed) using data from our preliminary *in vitro* experiments:

Variable	Mean±SD Lean Serum	n	Mean±SD Obese Serum	n	Power
MCP-1 mRNA	1.18±0.18	12	2.3±0.6	12	0.88
IL-6 mRNA	0.6±0.06	12	1.2±0.06	12	0.99

**Other specific methods:** **Intestinal permeability test.** Five g lactulose and two g mannitol dissolved in water are ingested, hourly urine and plasma samples are collected for 8 hours, and lactulose and mannitol are analyzed by gas chromatography (66, 67). Lactulose and mannitol permeate only in minimal amounts across the normal intestinal wall and are not metabolized by the body. In disease state, the intestine becomes preferentially permeable to lactulose than mannitol. [name] (Co-I) has previously conducted this test (68).

**Metagenomics.** The metagenomics experiments will be carried out by [name] (Co-I), as described by his group (69-71). DNA is extracted using a kit from MoBio (Carlsbad, CA) and following the protocol established by the Human Microbiome Project Consortium (72). PCR-amplified 16S rDNA is sequenced using the Illumina HiSeq2000 platform, following the sequencing and data processing protocol designed by Caporaso (73). Taxonomy is assigned to each high-quality read based on the best matching Greengenes database sequence (74). Operational Taxonomic Units are clustered by using the QIIME toolkit (75). For Aim 1, ANOVA and t-test (and their non-parametric versions) and Chi-square/Fisher's exact test are applied to detect taxa with significantly different relative abundance either within the same individuals (*i.e.*, low fat vs. high fat) or between treatments (placebo, synbiotic, sevelamer). Shannon, UniFrac, and Bray-Curtis indices are compared to quantify the community-level variability among the samples within and between individuals. Multiple test corrections (*e.g.*, Benjamini-Hochberg-Yekutieli) are applied to control for false discovery rate. The response variable (microbial composition) is analyzed with the explanatory variables (insulin sensitivity, LPS level, etc.) to evaluate for associations by Generalized linear models. Models also are used for analyzing the influence of explanatory variables on the relative abundance of significantly changing bacterial taxa (or) communities with treatments. For Aim 2, the data analysis and comparisons between groups (obese, T2DM, and lean) and treatments (placebo, synbiotic, sevelamer) are done similarly as in Aim 1.

**Summary/Timetable.** We are very excited about this proposal which will study the role that the microbiome and endotoxemia play a key role in the pathogenesis of insulin resistance. The studies proposed are innovative because the role of the microbiome on insulin resistance is unclear and relevant because they could lead to the development of novel therapies for T2DM. This application describes a 3 year program:

Year 1: Start Aim 1      Year 2: Complete Aim 1; Start Aims 2 and 3      Year 3: Complete Aims 2 and 3

**Risks:** a) Muscle biopsy: Local hematomas occur in <2% of subjects. b) Sevelamer: This drug is FDA approved for use as a phosphate binder. Sevelamer does not cause hypophosphatemia in subjects with normal kidney function (71, 76). As a precaution, we will only enroll subjects with normal phosphorus plasma concentration, which will be monitored during treatment. Sevelamer is a very safe drug; its main side effects are gastrointestinal. Subjects with a history of gastrointestinal obstruction and/or surgery within 2 years will be excluded. c) Oligofructose and Bididobacteria administration is very safe. Rarely these can cause bloating.

